13. STATISTICS

13.1. Statistical Analysis

This section presents a summary of the planned statistical analyses. A SAP that describes the details of the analyses to be conducted will be written prior to database lock.

Unless otherwise indicated, all testing of statistical significance will be two-sided, and a difference resulting in a P value of ≤ 0.05 will be considered statistically significant.

Summary statistics will be provided for the variables described below. For continuous variables, these statistics will include the number of subjects, mean, standard deviation (SD), median, minimum, and maximum. For categorical variables, these statistics will include the number and percentage of subjects in each category.

The primary analysis period is the first 90 days of treatment (i.e., the Double-blind Period). Overall unblinding will take place at the end of the Double-blind Period of the study only after the database is locked. A second analysis will take place for endpoints assessed from Day 90 through the OLE Period. The baseline for the safety and efficacy parameters will be measured at Visit 1 or Visit 2, per the Schedule of Events for both the Double-blind Period ([Table 2-1](#)) and OLE ([Table 2-2](#)).

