13.1.6.2 Adverse Events

All AEs will be coded using the Medical Dictionary for Regulatory Activities (MedDRA), Version 20.1 or higher.

Treatment-emergent AEs are defined as:

- AEs with onset at the time of or following the start of treatment with IP through the Follow-up Visit or Early Termination Visit, whichever occurs first, or
- AEs starting prior to the start of treatment but increasing in severity or relationship at the time of, or following, the start of treatment with IP through the Follow-up Visit or Early Termination Visit, whichever occurs first.

The number and percentage of subjects with AEs will be displayed by each treatment group in the Double-blind Period and overall in the OLE by system organ class and preferred term. Summaries of AEs by severity and relationship to IP will also be provided. Serious adverse events and AEs resulting in discontinuation of IP will be summarized separately in a similar manner. Subject listings of AEs, SAEs, and AEs causing discontinuation of IP will be produced.

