13.1.6.3 Clinical Laboratory Evaluations

Descriptive summaries (mean, SD, median, minimum, and maximum) of actual (absolute) values and changes from baseline values will be presented for clinical laboratory values for each treatment group at each time point in each period.

The number of subjects with clinical laboratory values categorized as below, within, or above normal ranges will be tabulated showing change from baseline (shift tables) for each clinical laboratory parameter by treatment group and by study visit in each period.

Laboratory values that are outside the normal range will also be flagged in the data listings and presented with the corresponding normal ranges. Any out-of-range values that are identified by the investigator as being clinically significant will also be shown in a data listing.

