13.1.6.4 Vital Signs

Descriptive summaries (mean, SD, median, minimum, and maximum) of actual values and changes from baseline will be calculated for SBP, DBP, and pulse for each period.

The number of subjects with vital signs values categorized as below, within, or above normal ranges will be tabulated showing change from baseline (shift tables) for each parameter by period, by treatment group and by study visit. Pre and post-treatment values may also be presented with an analysis of mean changes from baseline.

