	
The PK population includes all subjects in the Safety Population who have at least 1 plasma sample with quantifiable concentration. The PK population will be used to summarize all PK endpoints.
 
The following populations are planned for the OLE of this study:
 
The OLE Safety population: all subjects who complete the 12-week Double-blind Treatment Period and receive at least 1 application of study drug in the OLE.
 
OLE ITT population: all subjects who complete the 12-week Double-blind Period and who sign the OLE informed consent.
 
The OLE mITT population: all subjects in the OLE safety population with at least 1 assessment of efficacy after Visit 6.
 
The OLE PP population: all subjects in the OLE mITT population who met all inclusion criteria and no exclusion criteria, were compliant with study drug application from baseline through EOT, and who had no significant protocol deviations throughout the study.
 
Subject Characteristics and Disposition: Descriptive statistics will be used to summarize demographic characteristics (age, sex, ethnicity, and race) and baseline characteristics for all enrolled subjects. Medical history, physical examination findings, and vital sign measurements for all randomized subjects will be presented in listings.
 
Efficacy Analyses: The number and proportion of subjects in each treatment group with successful resolution of LI by Week 12/EOT in the Double-blind Period will be presented. The primary efficacy endpoint will be analyzed using a logistic regression model with treatment and age group as factors. Other baseline characteristics and interactions may be included. The odds ratios and 95% CIs for the odds ratios will be presented. The difference in proportions between the active trifarotene cream HEI and vehicle cream groups, 95% CIs for the differences, and P-values for the differences in treatment will also be presented.
 
The IGA scores as well as secondary and exploratory efficacy endpoints will be analyzed by visit using descriptive statistics through Week 24. Change from Baseline through Week 12 will be presented and analyzed using a mixed model for repeated measures (MMRM). The model will include the change from Baseline score as the dependent variable, treatment group as a fixed effect, subject as a random effect, and Baseline score value as a covariate. Frequencies of results and 95% confidence intervals will also be reported, and scores will be analyzed as categorical variables using the Cochran-Mantel-Haenszel test. For subjects who report having fissures, the number of fissures and pain related to fissures will also be presented on a scale of 0-3 (none, mild, moderate, severe).
 
Clinical Pharmacology Analyses: Noncompartmental PK analysis will be performed for the PK subset of subjects, as data permit. Plasma concentrations of CD5789 and its major metabolites will be measured and will be listed by subject.
 
Safety Analyses: Safety and tolerability will be assessed based on the incidence of reported TEAEs, and SAEs, including relationship to study drug and severity, as well as physical examination findings, vital sign measurements (supine systolic blood pressure [SBP] and diastolic blood pressure [DBP] and pulse), clinical laboratory results (hematology, including serum aminotransferases and serum lipids, coagulation, clinical chemistry, and urinalysis) and 12-lead ECGs. Descriptive statistics for observed values and change from Baseline will be calculated at each visit within each study period and by treatment group within cohort.

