9.6. Method of Assigning Subjects to Treatment Groups

In the double-blind, parallel-group, randomized period of the study, subjects who meet study entry criteria will be randomly assigned in a 1:1:1 ratio to trifarotene cream HE1 100 µg/g or 200 µg/g or vehicle cream. The randomization schedule will be computer generated using a permuted block algorithm and will randomly allocate IP to randomization numbers. The randomization numbers will be assigned sequentially through a central interactive web response system (IWRS) as subjects are entered into the study. Study center will not be a blocking factor in the randomization schedule.

Premier Research will prepare the randomization schedule before the start of the study. No one involved in the study performance will have access to the randomization schedule before the official unblinding of treatment assignments. No subject will be randomized into this study more than once.

In the OLE, all subjects will receive trifarotene cream HE1 200 µg/g.

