10.2.2.7 Visit 6 (90 ±7 days) or Early Termination

The following procedures will be performed on Day 90 in the study clinic:

1. Record responses to DLQI and EQ-5D Quality of Life Questionnaires.
2. Perform a physical examination.
3. Record vital signs (blood pressure and pulse).
4. Record concomitant medications and concomitant therapies.
5. Record IGA.
6. Record VIIS.
7. Record roughness assessment.
8. Record palm/sole assessment.
9. Record palm/sole assessment of fissuring.
10. Record ectropion score.
11. At sites where the optional photographic substudy is conducted, take photographs of subjects who have provided informed consent for the substudy.
12. Assess local tolerance.
13. Record AEs and review diary.
14. Perform a 12-lead ECG.
15. Perform a urine pregnancy test for WOCBP.
16. Collect blood and urine for routine laboratory tests (subject must be fasting at least 8 hours).
17. Collect a PK blood sample (all subjects).
18. Collect returned study drug tubes; confirm study drug compliance by weighing returned tube contents and reviewing diaries.

For subjects who successfully complete (i.e., have reliable visit attendance and compliance with IP application, in the investigator's opinion) the initial 12 weeks of double-blind treatment and choose to continue into the OLE, this visit will be the first visit of that portion of the study. All efficacy assessments, safety/tolerability assessments, including clinical laboratory testing, PK from Day 90/Week 12 will be carried over to the OLE and will not be repeated. Subjects will have up to 7 days to decide to enter the OLE; if the subject chooses to continue into OLE, the following additional procedures will be done:

1. Have the subject sign OLE-specific informed consent.
2. Measure subject's weight.
3. Instruct subject on study drug application, and advise subjects regarding permitted emollient(s) and/or sunscreen for use on nontreatment days; use of emollient(s) on study drug treatment days within 4 hours before or after study drug application is prohibited. Remind subjects that at least 24 hours must have elapsed since IP application before the

PK draws at the Week 16 and Week 24 Visits, and not to apply IP on visit days until after the visits.

4. Weigh new study drug tubes and dispense enough additional study drug until next visit (only for subjects who choose to continue into the OLE).
5. Dispense study diary.

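### The OLE safety baseline is fixed at Visit 1 or Visit 2, so OLE laboratory and vital-sign changes and shifts in vehicle-randomised subjects include about 90 days on vehicle (minor)

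*Protocol*

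**What the plan says.** The later text of Section 13.1 gives one rule for the reference value: "The baseline for the safety and efficacy parameters will be measured at Visit 1 or Visit 2", with the schedules of both the Double-blind Period and the OLE named in the same sentence. No section shown defines a separate OLE baseline.

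Two sections use that baseline in the OLE. For laboratory categories (Section 13.1.6.3), counts "will be tabulated showing change from baseline (shift tables) for each clinical laboratory parameter by treatment group and by study visit in each period". For vital signs (Section 13.1.6.4), counts "will be tabulated showing change from baseline (shift tables) for each parameter by period, by treatment group and by study visit". Both sections also plan descriptive changes from baseline in each period.

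On treatment, Section 9.6 states: "In the OLE, all subjects will receive trifarotene cream HE1" 200 µg/g. That includes subjects who were on vehicle until Day 90.

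Section 10.2.2.7 and the consent footnote to Table 2-2 make Day 90 the first OLE visit and carry its assessments forward without repeating them. They do not call Day 90 a baseline.

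The visit schedule and Sections 6.2, 9 and 10 are read from the Amendment 2 text, because the later Table 2-2 is not shown. The visit numbers agree with the later Appendix B.

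**The concern.** Safety on open-label 200 µg/g is a secondary objective (Section 6.2). For a subject randomised to vehicle, the natural reference for that question is the last value before any trifarotene. Under the Section 13.1 rule the reference is the value at study entry, so the OLE tables attach to the open-label period whatever happened on vehicle. In a shift table this can go wrong in two directions: a shift from vehicle time can be carried into the OLE count, or a worsening on drug can be hidden because the entry value was already abnormal.

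**Working it through.** The plan gives no figure to reproduce here. The check is a reading of the baseline rule against the treatment sequence, plus day arithmetic.

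**Inputs.** Baseline at Visit 1 (Screening, taken at its Day −35 limit) or Visit 2 (Day 1); vehicle from Day 1 to Day 90; OLE laboratory tests at Days 120 and 180 (Table 2-2); OLE vital signs at Days 104, 120, 150, 180 and 194 (Sections 10.2.4.2 to 10.2.4.7). Day 194 is the follow-up visit, 14 days after the last application.

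**Formula.** Vehicle share of the change window = (90 − 1) / (visit day − baseline day).

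| OLE visit | Share from Day 1 | Share from Day −35 | Days since Day 90 |
|---|---|---|---|
| Day 104 | 89/103 = 86% | 89/139 = 64% | 14 |
| Day 120 | 89/119 = 75% | 89/155 = 57% | 30 |
| Day 150 | 89/149 = 60% | 89/185 = 48% | 60 |
| Day 180 | 89/179 = 50% | 89/215 = 41% | 90 |
| Day 194 | 89/193 = 46% | 89/229 = 39% | 104 |

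If the subject uses the 7 days allowed for deciding on the OLE, time before any trifarotene is (97 − 1)/(120 − 1) = 81% at Day 120 and (97 − 1)/(180 − 1) = 54% at Day 180, counted from Day 1. With a Day 90 baseline the vehicle share is 0% at every visit. These are shares of calendar time only.

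**What happens in a shift table for a vehicle-randomised subject:**

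| Entry | Day 90 (vehicle) | Day 120 (200 µg/g) | Tabulated from Visit 1/2 | From last value before trifarotene |
|---|---|---|---|---|
| Normal | High | High | Normal-to-high | High-to-high |
| High | Normal | High | High-to-high | Normal-to-high |

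In the first row nothing changed category on drug, yet an OLE shift is counted. In the second row the category worsened on drug and no shift is counted.

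**What can be recovered.** Section 13.1.6.3 plans actual values as well as changes at each time point. In the same subjects, mean(Day 120 − Day 90) = mean(Day 120) − mean(Day 90), so the mean change on drug follows by subtraction. The shift category does not: the Day 90 and Day 120 tables give separate counts, not the joint movement of each subject.

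**The case against.** The strongest reply is that Day 90 already belongs to the OLE. Section 13.1 starts the second analysis at Day 90, Section 10.2.2.7 calls that visit the first of the OLE, and its data are carried over. OLE tables read that way would show Day 90 next to Days 120 and 180. This stands. A reader might infer from the baseline rule that the OLE tables cannot separate vehicle time from 200 µg/g time. The documents do not support that: group means can be differenced, and movement in the category counts between Day 90 and later visits can be seen. Only the link within a subject is missing.

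That link can in part be found elsewhere: "Laboratory values that are outside the normal range will also be flagged in the data listings and presented with the corresponding normal ranges". Clinically significant laboratory changes must be reported as adverse events (Section 10.3.4.1.3), and clinically significant liver or lipid changes stop treatment (Section 9.4.1). This also stands. Section 13.1.6.4 mentions no flagged listing for vital signs, although Section 11.2.1 makes clinically relevant observations adverse events.

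It can also be said that change from study entry is a legitimate quantity, since it shows cumulative change for active-origin subjects and keeps the OLE comparable with the double-blind tables. That is right, and it is why the display should be kept rather than replaced.

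Two further replies carry less weight. The SAP could add an OLE baseline, but the protocol sentence expressly fixes Visit 1 or 2 for both periods, so this is a stated rule rather than a missing detail. Subjects randomised to 100 µg/g also change dose at Day 90, and the remedy leaves that mixture in place. This is true, but it is a mixture of two doses of drug, not of drug and no drug.

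**Conclusion.** The point holds as a minor one. For vehicle-randomised subjects, the OLE laboratory and vital-sign changes and shifts include about 90 days on vehicle, and individual shift categories can be misplaced in either direction. No test or stopping decision depends on these tables, and Section 13.1.6 excludes inference on safety variables. The loss is mainly the within-subject shift category in one arm. That arm would be about a third of OLE entrants if entry is equal across arms, which is an assumption: 40 of 120 with no loss, or 32 of 96 if the 20% allowance is read as non-completion.

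A reader might take the 75% and 50% shares at Days 120 and 180 as the size of a bias. They are not: the documents give no rate of shifts on vehicle, so no number of misplaced shifts can be stated. A reader might also extend the point to ECG, but the later Section 13.1.6.5 plans no ECG change from baseline.

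The conclusion rests on the Amendment 2 schedule still applying and on no separate OLE baseline being set in text that is not shown.

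**What to change.** Add one sentence to Section 13.1: for subjects randomised to vehicle, OLE laboratory and vital-sign changes and shifts are also presented from the last value before the first trifarotene application, which is Day 90, or the last earlier value if Day 90 is missing (Appendix B lets Visit 6 be remote). Show these by randomised arm, do not pool them with active-origin subjects, and keep the Visit 1/2 display for all arms.

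No new data are needed. Section 10.2.2.7 already schedules Day 90 vital signs and laboratory tests ("Collect blood and urine for routine laboratory tests (subject must be fasting at least 8 hours"). The cost is one derived baseline flag and one more set of descriptive tables. The downside is that intervals then depend on the arm: at Day 180, about 90 days for vehicle-origin subjects against about 180 days for the others. That is the reason for not pooling.

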13.1.1 Analysis Populations

The following 5 analysis populations are planned for the Double-blind Period of this study:

- Safety: all subjects who are randomized to treatment and receive at least 1 application of study drug in the Double-blind Period. This population will be the primary population for analyses of safety.
- Intent-to-treat (ITT): all randomized subjects. This population will be used as the primary population for the analysis of efficacy for the Double-blind Period of the study.
- Modified intent-to-treat (mITT): all subjects in the safety population with at least 1 postbaseline assessment of efficacy in the Double-blind Period.
- Per-protocol (PP): subjects in the mITT Population who met all inclusion criteria and no exclusion criteria, were compliant with study drug application, and who had no significant protocol deviations.
- Pharmacokinetic: all subjects in the Safety Population who have at least 1 plasma sample with quantifiable concentration. This population will be used to summarize all PK endpoints.

The following analysis populations are planned for the OLE of this study:

- OLE Safety: all subjects who complete the 90-day Double-blind Treatment Period and receive at least 1 application of study drug in the OLE.
- OLE ITT: all subjects who complete the 90-day Double-blind Treatment Period and sign the OLE informed consent.
- OLE mITT: all subjects in the OLE safety population with at least 1 assessment of efficacy after Visit 6.
- OLE PP: all subjects in the OLE mITT population who met all inclusion criteria and no exclusion criteria, were compliant with study drug application from baseline through EOT, and who had no significant protocol deviations throughout the study.

Inclusion in the analysis populations will be determined prior to database lock. Deviations related to COVID-19 will also be evaluated in determining PP population eligibility.

If a subject is randomized incorrectly or is administered the incorrect IP, analyses of the ITT and mITT populations will be based on the assigned treatment whereas all other analyses will be based on the actual treatment received.

13.1.2 Study Subjects and Demographics

13.1.2.1 Disposition and Withdrawals

For the Double-blind Period, the numbers of subjects randomized, completing Day 90 of the study, and withdrawing early from the Double-blind Period, along with reasons for withdrawal, will be tabulated overall and by randomized treatment group. The number of subjects in each analysis population will be reported. The number of subjects completing study milestones will also be tabulated by randomized treatment group. This analysis will be conducted for the ITT population.

For the OLE, the number of subjects entering the OLE, completing the study, and withdrawing early, along with reasons for withdrawal, will be tabulated overall. The number of subjects in each analysis population will be reported. The number of subjects completing study milestones will also be tabulated. This analysis will be conducted for the OLE ITT population.

13.1.2.2 Protocol Deviations

A protocol deviation is any noncompliance with the clinical study protocol or International Council for Harmonisation of Technical Requirements for Pharmaceuticals for Human Use (ICH) Good Clinical Practice (GCP) requirements. The noncompliance may be either on the part of the participant, the investigator, or the study site staff. As a result of deviations, corrective actions are to be developed by the site and implemented promptly.

It is the responsibility of the site investigator to use continuous vigilance to identify and report deviations promptly. All deviations must be addressed in study source documents, and reported to Premier Research or Mayne Pharma LLC. Protocol deviations must be sent to the reviewing IRB per their policies. The site investigator is responsible for knowing and adhering to the reviewing IRB requirements. Further details about the handling of protocol deviations will be included in the protocol deviation guidance plan.

Subjects who taper to once-weekly application or who take a “drug holiday” will not be reported as having deviated from the protocol.

13.1.2.3 Demographics and Other Baseline Characteristics

These analyses will be conducted for the ITT and OLE ITT populations.

Demographic variables will include age, sex, race, ethnicity, height, weight, and BMI. Baseline subject characteristics will include medical history, physical examination findings, and IGA score.

Prior and concomitant medications will be summarized by randomized treatment group, by the number and percentage of subjects taking each medication, and classified using World Health Organization Drug Dictionary (WHO-DD) Anatomical Therapeutic Chemical (ATC) classes and preferred terms.

13.1.3 Exposure and Compliance

Investigational product administration will be summarized in terms of each subject’s dose, and in terms of duration of exposure for each period. Descriptive statistics for these quantities, including the mean, median, SD, minimum, maximum, and quartiles, will be provided by treatment group.

Additionally, the number of subjects who are compliant with investigational product will be presented by treatment group for the Double-blind Period and overall for the OLE.

Subjects who taper to once-weekly application or who take a “drug holiday” will not be reported as having deviated from the protocol.

